## 7.2 Cobimetinib plus Atezolizumab and CDX-1127 (varlilumab) (Treatment Arm A patients only)

### 7.2.1 Recommended Cobimetinib Dose Modifications

In order to standardize the management of AEs, suggested treatment management algorithms for adverse events of particular concern for cobimetinib plus atezolizumab & CDX-1127 (varlilumab) are included in Section 7.3. The following general dose modifications table for cobimetinib is for AEs not specified in the subsequent tables.

| Grade (CTCAE) a  | Recommended Cobimetinib Dose   |
|---|--|
| Grade 1 or Grade 2 (tolerable)  | No dose reduction. Maintain cobimetinib at a dose of 60 mg QD (3 tablets)            |
| Grade 2 (intolerable) or Grade 3 b or 4 (any)
First appearance | Interrupt treatment until Grade $\leq 1$ , restart treatment at 40 mg QD (2 tablets) |
| Second appearance  | Interrupt treatment until Grade $\leq 1$ , restart treatment at 20 mg QD (1 tablet)  |
| Third appearance   | Consider permanent discontinuation   |

CTCAE = Common Terminology Criteria for Adverse Events; NCI = National Cancer Institute; QD = once daily.

a The intensity of clinical adverse events graded by NCI CTCAE v5.0.

b An exception to this is for Grade 3 anemia, without presence of hemorrhage and/or hemolytic process. In this case, participants can be treated with transfusions as needed in order to improve to grade 2 or better and do not require treatment interruption or dose

reduction. If recurrent transfusions are needed, treating provider can consider dose reduction.

Toxicities will be evaluated using NCI CTCAE v5.0. If toxicity occurs, the toxicity will be graded and appropriate supportive care treatment will be administered to decrease symptoms.

Generally, in the case of Grade 4 hematologic or Grade 3 to 4 non-hematologic toxicity (except for Grade 3 skin cancer, squamous or basal cell type), treatment with cobimetinib should be interrupted until recovery to baseline or Grade 1 and then resumed at one dose level reduction. Below is a table for cobimetinib dosing upon dose modification:

| Dose level | Dose                             |
|------------|----------------------------------|
| 0          | 60 mg QD 21 days out of 28 days  |
| (-1)       | 40 mg QD, 21 days out of 28 days |
| (-2)       | 20 mg QD, 21 days out of 28 days |

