### **7.3 AE Management and Dose Interruption/Modification Guidelines**

| AE Management and Dose Interruption Guidelines for Specific Toxicities |                         |   |   |
|--|-------------------------|---|---|
| Toxicity   | Severity/
Duration   | Management  |   |
|  |                         | CDX-1127 (varlilumab)
& Atezolizumab   | Cobimetinib plus
CDX-1127 (varlilumab)
& Atezolizumab   |
| Abdominal pain   | Acute
abdominal pain | Symptoms of abdominal pain associated with elevations of amylase and lipase, suggestive of pancreatitis, have been associated with administration of other immunomodulatory agents. The differential diagnosis of acute abdominal pain should include pancreatitis. Appropriate workup should include an evaluation for | Symptoms of abdominal pain associated with elevations of amylase and lipase, suggestive of pancreatitis, have been associated with administration of other immunomodulatory agents. The differential diagnosis of acute abdominal pain should include pancreatitis. Appropriate workup should include an evaluation for |

|   |                        |   |  |
|---|------------------------|---|--|
|   |                        | 
obstruction, as well as serum amylase and lipase tests. See the guidelines for “Amylase and/or lipase increase” and “Immune-related pancreatitis” elsewhere in this table, as needed.
 
Right upper-quadrant abdominal pain and/or unexplained nausea or vomiting should be evaluated for potential hepatotoxicity (see the “Hepatotoxicity” guideline elsewhere in this table).
  | 
obstruction, as well as serum amylase and lipase tests. See the guidelines for “Amylase and/or lipase increase” and “Immune-related pancreatitis” elsewhere in this table, as needed.
 
Right upper-quadrant abdominal pain and/or unexplained nausea or vomiting should be evaluated for potential hepatotoxicity (see the “Hepatotoxicity” guideline elsewhere in this table).
   |

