|                                 | Grade 2      | 
Continue atezolizumab & CDX-1127 (varlilumab).
 
Monitor amylase and lipase weekly.
 
For prolonged elevation (e.g., >3 weeks), consider treatment with 10 mg/day oral prednisone or equivalent.
 
Asymptomatic with amylase and/or lipase >2.0–5.0 × ULN:
Treat as a Grade 3 event.
 | 
Continue atezolizumab & CDX-1127 (varlilumab) and cobimetinib.
 
Monitor amylase and lipase weekly.
 
For prolonged elevation (e.g., >3 weeks), consider treatment with 10 mg/day oral prednisone or equivalent.
 
Asymptomatic with amylase and/or lipase >2.0–5.0 × ULN:
Treat as a Grade 3 event.
 |
|                                 | Grade 3 or 4 | Hold atezolizumab & CDX-1127 (varlilumab).  | Hold atezolizumab & CDX-1127 (varlilumab) and cobimetinib.  |

|        |   |  |  |
|--------|---|--|--|
|        |   | 
Refer patient to gastrointestinal (GI) specialist.
 
Monitor amylase and lipase every other day.
 
If no improvement, consider treatment with 1–2 mg/kg/day oral prednisone or equivalent.
 
If event resolves to grade 1 or better within 12 weeks, taper corticosteroids and resume atezolizumab & CDX-1127 (varlilumab) according to the guidelines above.
 
Permanently discontinue atezolizumab & CDX-1127 (varlilumab) if event does not resolve to grade 1 or better within 12 weeks.
 
For recurrent events, permanently discontinue atezolizumab & CDX-1127 (varlilumab).
 | 
Refer patient to gastrointestinal (GI) specialist.
 
Monitor amylase and lipase every other day.
 
If no improvement, consider treatment with 1–2 mg/kg/day oral prednisone or equivalent.
 
If event resolves to grade 1 or better within 12 weeks, taper corticosteroids and resume atezolizumab & CDX-1127 (varlilumab) at previous fixed and cobimetinib with 1 dose-level reduction.
 
Permanently discontinue atezolizumab & CDX-1127 (varlilumab) and cobimetinib if event does not resolve to grade 1 or better within 12 weeks.
 
For recurrent events, permanently discontinue atezolizumab & CDX-1127 (varlilumab) and cobimetinib.
 |

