| Pancreatitis,
immune related | Grade 2 or 3 | 
Hold atezolizumab & CDX-1127 (varlilumab)
 
Refer patient to GI specialist.
 
Initiate treatment with 1–2 mg/kg/day intravenous methylprednisolone or equivalent and convert to 1–2 mg/kg/day oral prednisone or equivalent upon improvement.
 
If event resolves to grade 1 or better within 12 weeks, taper corticosteroids and resume atezolizumab & CDX-1127 (varlilumab) according to the guidelines above.
 
Permanently discontinue atezolizumab & CDX-1127 (varlilumab) if event does not resolve to grade 1 or better within 12 weeks. Patient may only resume treatment after consultation with the trial PI.
 
For recurrent events, permanently discontinue atezolizumab & CDX-1127 (varlilumab). Patient may not resume treatment, regardless of benefit.
 | 
Hold atezolizumab & CDX-1127 (varlilumab) and cobimetinib
 
Refer patient to GI specialist.
 
Initiate treatment with 1–2 mg/kg/day intravenous methylprednisolone or equivalent and convert to 1–2 mg/kg/day oral prednisone or equivalent upon improvement.
 
If event resolves to grade 1 or better within 12 weeks, taper corticosteroids and resume atezolizumab & CDX-1127 (varlilumab) and cobimetinib at same doses.
 
Permanently discontinue atezolizumab & CDX-1127 (varlilumab) and cobimetinib if event does not resolve to grade 1 or better within 12 weeks.
 
Patient may only resume treatment after consultation with the trial PI.
 
For recurrent events, permanently discontinue atezolizumab & CDX-1127 (varlilumab) and cobimetinib. Patient may not resume treatment, regardless of benefit.
 |
|---------------------------------|--------------|---|--|

|                    |                      |  |  |
|--------------------|----------------------|--|--|

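### Section 7.3, Arm A: a patient with Grade 3–4 amylase/lipase elevation and Grade 2–3 immune-related pancreatitis meets two rows that restart cobimetinib at different doses, and no rule says which governs

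*Combined protocol and SAP*

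**What the plan says.** Three rows of the table in Section 7.3 are involved, read in the column for cobimetinib plus the two antibodies (Arm A).

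- **Abdominal pain.** Pain with raised amylase and lipase is described as suggestive of pancreatitis. The row continues: "See the guidelines for “Amylase and/or lipase increase” and “Immune-related pancreatitis” elsewhere in this table, as needed".
- **Amylase and/or lipase increased, Grade 3 or 4.** All three agents are held. If the event settles to Grade 1 or lower inside 12 weeks, the antibodies resume "at previous fixed and cobimetinib with 1 dose-level reduction". An asymptomatic Grade 2 rise above 2.0–5.0 × ULN carries the instruction "Treat as a Grade 3 event".
- **Pancreatitis, immune related, Grade 2 or 3.** All three agents are held. On the same recovery condition the antibodies resume "and cobimetinib at same doses".

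Section 7.2.1 gives general cobimetinib rules. Of its table it says: "The following general dose modifications table for cobimetinib is for AEs not specified in the subsequent tables". A separate sentence, introduced as a general rule for Grade 3–4 non-hematologic toxicity, says "treatment with cobimetinib should be interrupted until recovery to baseline or Grade 1 and then resumed at one dose level reduction".

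**The concern.** Raised enzymes and pancreatitis are not separate populations. The abdominal pain row itself links them and sends the site to both sets of guidance. The enzyme row does not exclude patients who have pancreatitis, and the pancreatitis row does not mention enzyme grade. One patient can therefore satisfy both rows, meet the same recovery condition in each, and be given two different cobimetinib doses.

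What is at stake is that patient's dose of the drug that distinguishes Arm A from Arm B. The number of reductions left also depends on the row used, because 7.2.1 permits only two and the enzyme row uses one.

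The rows may also differ when the event has not settled by 12 weeks. Both call for permanent discontinuation, but the pancreatitis row adds a sentence allowing resumption only after consultation with the trial PI. The enzyme row has no such sentence.

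**Working it through.** No sample size, power or error-rate calculation is involved. The check compares the texts, with simple dose arithmetic.

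**Step 1. The two rows for the same Arm A patient**

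| | Enzymes, Grade 3–4 | Immune-related pancreatitis, Grade 2–3 |
|---|---|---|
| Initial action | Hold all three agents | Hold all three agents |
| Recovery condition | Grade 1 or lower inside 12 weeks | Grade 1 or lower inside 12 weeks |
| Cobimetinib at restart | One level lower | Same dose |
| Not settled at 12 weeks | Permanent discontinuation | Permanent discontinuation, plus a PI-consultation sentence |
| Recurrence | Permanent discontinuation | Permanent discontinuation, no resumption whatever the benefit |

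The actions agree until restart, where the doses cannot both be followed.

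**Step 2. Does any other text break the tie?**

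- The 7.2.1 table is confined to events not covered later. Both events are covered in 7.3, so it does not apply.
- The general Grade 3–4 sentence in 7.2.1 calls for a one-level reduction. For Grade 3 pancreatitis it therefore differs from the pancreatitis row as well. Nothing says whether it yields to that row.
- Section 7.2.2 asks sites to attribute an event to the targeted drug or the immunotherapy. Where attribution is unclear, it refers back to 7.3 for resumption.
- The hepatotoxicity row says that acute abdominal pain should prompt consideration of pancreatitis and points further down the table. It sets no precedence.

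**Step 3. Size for one patient**

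Inputs are the dose levels in 7.2.1 (60, 40 and 20 mg daily, 21 days in 28). Dose per cycle = daily dose × 21. The 60 mg result matches the example in the Appendix E diary.

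| Dose before event | Pancreatitis row | Enzyme row | Difference |
|---|---|---|---|
| 60 mg | 60 × 21 = 1260 mg | 40 × 21 = 840 mg | 420/1260 = 33% |
| 40 mg | 40 × 21 = 840 mg | 20 × 21 = 420 mg | 420/840 = 50% |
| 20 mg | 20 × 21 = 420 mg | No lower level defined | – |

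**Step 4. How many patients?**

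The atezolizumab risk list in 10.1.1.1 puts pancreatitis under 3% and marks the lipase and amylase increases as under 3%. If 3% is taken as a ceiling and carried over to the 32 patients planned for Arm A (9.2), 0.03 × 32 = 0.96, or about one patient with any pancreatitis. The overlap also needs Grade 3–4 enzymes, recovery in time and a restart, so under this assumption it is smaller. The documents give no rate for the triplet, and 10.1.1.1 warns that combinations may behave differently.

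**The case against.** The strongest defence is that the rows are alternatives chosen by diagnosis. The abdominal pain row is about work-up, and it refers to the two sets of guidance only as needed. Once immune-related pancreatitis is diagnosed, there is a dedicated row for it. Section 9.5.1 likewise separates enzyme abnormalities without symptoms or signs from pancreatitis. This is a sensible reading and some sites will adopt it, but it is implied. No text tells the site to leave the enzyme row, whose grade criteria the patient still meets.

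A second defence is attribution: immune-related pancreatitis belongs to the antibodies, so cobimetinib need not change. The adrenal insufficiency/hypophysitis row also resumes cobimetinib at the same dose. However, pancreatitis, lipase increase and amylase increase all appear on the atezolizumab list and none is on the cobimetinib list, so attribution would treat the two rows alike. Nor is the pattern uniform, since the colitis, pneumonitis and myositis rows reduce cobimetinib. Attribution makes the difference plausible but does not establish that it was intended.

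A third point is that 7.2.1 calls the 7.3 algorithms suggested. That softens the conflict without resolving it.

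A reader might infer that the ordering is inverted, because an asymptomatic patient is reduced and a patient with clinical pancreatitis is not. The documents do not support calling that a contradiction. It compares different patients under different rows, and the asymptomatic instruction does not reach someone who came in with abdominal pain. The pancreatitis rows are also stricter elsewhere: they start IV methylprednisolone where the enzyme row only considers oral prednisone, and they end treatment at Grade 4 where Grade 4 enzymes may restart. Whether the ordering is intended is a question for the sponsor.

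**Conclusion.** The conflict holds within narrow limits: Arm A, Grade 3–4 enzymes, Grade 2–3 immune-related pancreatitis, and recovery inside 12 weeks. Such a patient has two incompatible written restart instructions, 33% apart from 60 mg and 50% apart from 40 mg. No stated rule chooses between them, and for Grade 3 pancreatitis the general sentence in 7.2.1 adds a further disagreement. That is enough to warrant correction.

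Three wider readings are not supported.

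- A reader might infer that any raised lipase triggers the clash. It does not. For symptomatic overlap patients with Grade 1–2 enzymes, the mismatch is continuing against holding treatment, which is a different matter.
- A reader might infer uncontrolled exposure differences across Arm A. The listed single-agent rates are below 3% and no triplet rate is given, so a material trial-level effect is not shown.
- A reader might take the PI-consultation sentence as a settled route back only after 12 weeks. In the antibodies-only column it directly follows the 12-week rule. In the Arm A column it is a separate paragraph and could govern resumption more generally.

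The conclusion rests on the wording alone. The estimate that few patients are affected assumes that the atezolizumab rates are a rough guide to the triplet.

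**What to change.** Amend 7.3, and 7.2.1 where needed, to do the following:

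1. State which row governs when an enzyme elevation and immune-related pancreatitis are both present.
2. Reconcile the cobimetinib restart instruction between the two rows, and state whether the general Grade 3–4 sentence in 7.2.1 yields to the specific rows.
3. Make clear whether the PI-consultation sentence in the pancreatitis row applies only after non-resolution at 12 weeks, and how that fits with the enzyme row.
4. Say what the enzyme row means for a patient already at the lowest cobimetinib level.

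The sponsor should also confirm whether a reduction for enzyme elevation but not for clinical pancreatitis is intended. The choice of dose and rule is the sponsor's.

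The cost is a wording amendment to two table rows and a clarifying sentence in 7.2.1. Sample size, error rates and analyses are unaffected.

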| Anemia | Grade 3

Without presence of active hemorrhage or immune-mediated hemolysis | 
Continue atezolizumab & CDX-1127 (varlilumab).
 
Transfuse prn to Grade <math>\leq 2</math> or resolution of symptomatic anemia
 
Monitor CBC weekly
  | 
Continue atezolizumab & CDX-1127 (varlilumab) and cobimetinib
 
Transfuse prn to Grade <math>\leq 2</math> or resolution of symptomatic anemia
   |

|   |  |  |  |
|---|--|--|--|
|   |  | Workup for etiologies of anemia  | Monitor CBC weekly

Workup for etiologies of anemia

For recurrent grade 3 anemia, can consider 1 dose level reduction for cobimetinib   |
| Cardiac Event – Decreased Left Ventricular Ejection Fraction (LVEF) | Asymptomatic, absolute decrease in LVEF from baseline of greater than 10% and LVEF less than 50% | 
Hold atezolizumab & varlilumab. Assess for symptoms and complete work up. Repeat ECHO in 2 weeks.
 
Work up should generally include troponin, CPK, EKG, echocardiogram and/or cardiac MRI, and cardiology consultation
 
Resume atezolizumab & CDX-1127 (varlilumab) at fixed dose if all of the following are present
 
 
• LVEF is 50% or greater, OR
 
• Absolute decrease from baseline LVEF is more than 10%
 
 
Permanently discontinue atezolizumab & CDX-1127 (varlilumab)* if any of the following are present
 
 
• LVEF is 50% or greater, AND
 
• Absolute decrease from baseline LVEF is more than 10%
 
 
* If etiology of
 | 
Hold atezolizumab, CDX-1127 (varlilumab), and cobimetinib. Assess for symptoms and complete work up. Repeat ECHO in 2 weeks.
 
Work up should generally include troponin, CPK, EKG, echocardiogram and/or cardiac MRI, and cardiology consultation
 
Resume atezolizumab & CDX-1127 (varlilumab) at fixed dose and cobimetinib at next lower dose if all of the following are present
 
 
• LVEF is 50% or greater, OR
 
• Absolute decrease from baseline LVEF is more than 10%
 
 
Permanently discontinue atezolizumab & CDX-1127 (varlilumab)* and cobimetinib any of the following are present
 
 
• LVEF is 50% or greater, AND
 
• Absolute decrease from
 
 |

|  |   |  |   |
|--|---|--|---|

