|  |   | 
decreased LVEF can be confidently attributed to a non-immune-mediated etiology, LVEF is > 40% (or <math>\leq</math> 10% absolute decrease from BL) and myocarditis has been excluded, resumption of atezolizumab & CDX-1127 (varlilumab) at fixed dose can be considered on case by case basis with discussion & approval by trial PI. For patients with more severe reductions in the LVEF, atezolizumab & CDX-1127 (varlilumab) may be restarted only if the patient is clinically stable, and after consultation with the trial PI.
 | 
baseline LVEF is more than 10%
 
*If etiology of decreased LVEF can be confidently attributed to cobimetinib alone or a non-immune-mediated etiology, LVEF is > 40% (or <math>\leq</math> 10% absolute decrease from BL) and myocarditis has been excluded, resumption of atezolizumab & CDX-1127 (varlilumab) at fixed dose can be considered on case by case basis with discussion & approval by trial PI. For patients with more severe reductions in the LVEF, atezolizumab & CDX-1127 (varlilumab) may be restarted only if the patient is clinically stable, and after consultation with the trial PI.
 |
|  | Symptomatic LVEF decrease from baseline | 
Withhold atezolizumab & CDX-1127 (varlilumab) for up to 4 weeks; repeat LVEF
 
Work up should generally include troponin, CPK, EKG, echocardiogram and/or cardiac MRI, and cardiology consultation
 
Resume atezolizumab & CDX-1127 (varlilumab) at fixed dose if all of the following are present
 
 
• Symptoms
 
   | 
Withhold atezolizumab & CDX-1127 (varlilumab) and cobimetinib for up to 4 weeks; repeat LVEF
 
Work up should generally include troponin, CPK, EKG, echocardiogram and/or cardiac MRI, and cardiology consultation
 
Resume atezolizumab & CDX-1127 (varlilumab) at fixed dose and cobimetinib at next
   |

|  |  |  |   |
|--|--|--|---|

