|  |  | 
resolved, and
 
 
• LVEF is 50% or greater, OR
 
• Absolute decrease from baseline LVEF is 10% or less
 
 
Permanently discontinue atezolizumab & CDX-1127 (varlilumab)* if any of the following are present
 
 
• Symptoms persist, or
 
• Symptoms resolved, but LVEF is less than 50% and Absolute decrease from baseline LVEF is more than 10%
 
 
* If etiology of decreased LVEF can be confidently attributed to a non-immune-mediated etiology, LVEF is > 40% (or <math>\leq</math> 10% absolute decrease from BL) and myocarditis has been excluded, resumption of atezolizumab & CDX-1127 (varlilumab) at fixed dose can be considered on case by case basis with discussion & approval by trial PI. For patients with more severe reductions in the LVEF, atezolizumab & CDX-1127 (varlilumab) may be restarted only if the patient is clinically stable, and after
 | 
lower dose if all of the following are present
 
 
• Symptoms resolved, and
 
• LVEF is 50% or greater, OR
 
• Absolute decrease from baseline LVEF is 10% or less
 
 
Permanently discontinue atezolizumab & CDX-1127 (varlilumab)* and cobimetinib any of the following are present
 
 
• Symptoms persist, or
 
• Symptoms resolved, but LVEF is less than 50% and Absolute decrease from baseline LVEF is more than 10%
 
 
*If etiology of decreased LVEF can be confidently attributed to cobimetinib alone or a non-immune-mediated etiology , LVEF is > 40% (or <math>\leq</math> 10% absolute decrease from BL) and myocarditis has been excluded, resumption of atezolizumab & CDX-1127 (varlilumab) at fixed dose can be considered on case by case basis with discussion & approval by trial PI. For patients with more severe reductions in the LVEF,
 |
|--|--|--|---|

|                                 |   |   |   |
|---------------------------------|---|---|---|
|                                 |   | consultation with and approval from the trial PI.   | atezolizumab & CDX-1127 (varlilumab) may be restarted only if the patient is clinically stable, and after consultation with and approval from the trial PI.   |

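### Section 7.3, asymptomatic LVEF fall: the resume and permanent-stop rules use the same two comparisons, so LVEF at or above 50% with a fall over 10 points meets both and LVEF below 50% with a fall of 10 or less meets neither

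*Combined protocol and SAP*

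**What the plan says.** The Section 7.3 table has two rows for decreased LVEF, each with a column for the antibody doublet and a column for the triplet.

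**Asymptomatic row.** The hold is triggered by "Asymptomatic, absolute decrease in LVEF from baseline of greater than 10% and LVEF less than 50" per cent. After a work-up and a repeat echocardiogram, two rules apply:
- Resume (cobimetinib at the next lower dose in the triplet column). The lead-in requires *all* listed items, but the first item reads "LVEF is 50% or greater, OR". The second is "Absolute decrease from baseline LVEF is more than 10" per cent.
- Stop permanently. The lead-in requires *any* listed item, but the first item reads "LVEF is 50% or greater, AND". The second is again "Absolute decrease from baseline LVEF is more than 10" per cent.

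The wording is the same in both columns.

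**Symptomatic row.** The comparisons here are complementary. Once symptoms have resolved, treatment resumes at LVEF of 50% or more, or when "Absolute decrease from baseline LVEF is 10% or less" applies. It stops permanently if symptoms persist, or for "Symptoms resolved, but LVEF is less than 50% and Absolute decrease from baseline LVEF is more than 10" per cent.

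**Related text.** A starred note to the stop rule, beginning in the triplet column "If etiology of decreased LVEF can be confidently attributed to cobimetinib alone or a non-immune-mediated etiology", lets atezolizumab and varlilumab restart case by case with the trial PI's approval. It requires LVEF above 40% (or a fall of 10% or less) and myocarditis excluded. More severe reductions need a clinically stable patient and PI consultation. Section 7.2.2 sets the same conditions for the antibodies in Arm A. Neither covers restarting cobimetinib.

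**The concern.** A resume rule and a permanent-stop rule should divide the possible repeat-echo results between them. Two rules built on identical comparisons cannot do that. Two sites could re-dose one patient and permanently remove an identical one, each relying on the protocol.

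This row guides re-dosing in a triplet not previously given to humans (Section 2.3.4), and Section 2.2.2.2.3 describes cardiomyopathy as a known cobimetinib risk. For cobimetinib after an asymptomatic fall, no other text supplies an LVEF restart threshold:
- Section 7.2.2 addresses permanent cobimetinib discontinuation only for cardiac symptoms.
- The general cobimetinib table in Section 7.2.1 is for events without their own row.
- The Grade 3–4 paragraph in Section 7.2.1 is grade-based and gives no LVEF value.

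Arm A patients have scheduled post-baseline ECHO or MUGA (Section 11, note U), so sites will need the row. Arm B has the same bullets but no scheduled post-baseline LVEF check.

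**Working it through.** **Inputs** (Section 7.3, asymptomatic row). Let A be LVEF of 50% or more, and B be a fall from baseline of more than 10 points. Both rules combine A and B. Each rule's lead-in conflicts with its connector, so each can be read as A OR B, or as A AND B. That gives four readings.

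| Repeat result | Connectors as printed (resume OR, stop AND) | Resume OR, stop OR | Resume AND, stop AND | Lead-ins govern (resume AND, stop OR) |
|---|---|---|---|---|
| ≥50%, fall >10 | both | both | both | both |
| ≥50%, fall ≤10 | resume | both | neither | stop |
| <50%, fall >10 | resume | both | neither | stop |
| <50%, fall ≤10 | neither | neither | neither | neither |

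The first and last lines do not change with the reading. The middle two do:
- If the printed connectors govern, a patient still at the values that triggered the hold (third line) qualifies to resume and does not meet the stop rule.
- If the lead-ins govern, that patient stops, but a fully recovered patient (second line) is also told to stop permanently.

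**Where the fixed defects fall.** Eligibility requires a baseline LVEF above 50% (Section 3.1.5). For baseline b and repeat r, in whole percentages:
- Both rules met: 50 ≤ r < b − 10, which needs b > 60.
- Neither rule met: b − 10 ≤ r < 50, which needs b < 60.

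| Baseline | Both rules met | Neither rule met |
|---|---|---|
| 52% | – | 42–49% |
| 55% | – | 45–49% |
| 58% | – | 48–49% |
| 60% | – | – |
| 62% | 50–51% | – |
| 65% | 50–54% | – |
| 70% | 50–59% | – |

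Every eligible baseline except exactly 60% has one of the two bands.

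**No lower limit under the printed OR.** With baseline 65% and repeat 40%, the fall is 65 − 40 = 25 points, so B is true and A OR B is met. A is false, so A AND B is not met. On that reading the row lets cobimetinib resume.

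**Comparator.** The symptomatic row, with symptoms resolved and OR governing, gives resume = A OR (not B) and stop = (not A) AND B. In the table's line order the results are resume, resume, stop, resume. Each state meets exactly one rule.

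**The case against.** The strongest reply is that this is guidance to be used with judgement. Section 7.2 calls the algorithms suggested and recommended. The row asks for a repeat echocardiogram and a work-up that generally includes cardiology consultation. Section 10.3.4 makes left ventricular dysfunction of Grade 2 or worse an event of special interest for cobimetinib. Section 7.2.2 holds or discontinues all three agents when the responsible drug is unclear. A careful team would probably notice the misprint, since the next row is right. These points make harm less likely, but none states when cobimetinib may restart; for resumption, Section 7.2.2 points back to Section 7.3.

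Three stronger readings are tempting and are not supported:
- A reader might infer that the 65%-to-40% patient may resume all three drugs in Arm A. Section 7.2.2 and the starred note prevent that. A repeat of 40% is not above 40%, and a 25-point fall is not 10 or less, so the antibodies need a clinically stable patient and PI consultation. The example applies to cobimetinib only.
- A reader might infer that the protocol plainly tells sites to re-dose unrecovered patients. That depends on the printed OR overriding the lead-in.
- A reader might infer that the symptomatic row is equally defective. Its lead-in, "lower dose if all of the following are present", sits awkwardly with its OR, but the natural reading (symptoms resolved, and either LVEF condition) works.

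The statement in Section 2.2.2.2.3 about cobimetinib safety below 50% concerns baseline LVEF. It does not settle what on-treatment recovery should be required.

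**Conclusion.** The asymptomatic row is wrong as written. On every reading, one set of repeat-echo results meets both resume and permanent stop, and another meets neither. The second is less serious: the drugs stay on hold by default, and the antibodies have a case-by-case restart route. Either the unrecovered patient resumes (printed connectors) or the fully recovered patient stops (lead-ins), depending on which wording a site follows.

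The error looks like a drafting slip, because it is identical in both columns and the neighbouring row has the expected comparisons. The practical exposure is mainly cobimetinib in Arm A.

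The conclusion assumes that the absolute decrease is measured in LVEF percentage points; the bands also assume whole-number values. The documents give no rate for this trigger. The 26% LVEF-decrease figure in Section 2.2.2.2.3 comes from cobimetinib with vemurafenib and does not transfer, so no patient count is offered. No endpoint, sample size or analysis is affected.

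**What to change.** In both columns of the asymptomatic row:
- Resume, with cobimetinib at the next lower dose where it applies, if **either** LVEF is 50% or more **or** the absolute decrease is 10 points or less.
- Permanently discontinue if **both** LVEF is below 50% **and** the absolute decrease is more than 10 points.

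Keep the starred exception for atezolizumab and varlilumab. Change the lead-ins to agree with the connectors. In the symptomatic row, make the same tidy-up to the resume lead-in; its comparisons do not change.

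The sponsor's clinical team should confirm the cell with LVEF below 50% and a fall of 10 points or less, because this wording would re-dose cobimetinib below 50%.

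The cost is one amendment to the two LVEF rows and a notice to sites. Sample size, analysis and visit schedule are unchanged.
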